3.2 Exclusion Criteria

- Patients who have had chemotherapy within 1 week (6 weeks for nitrosoureas or mitomycin C) or investigational therapies/monoclonal antibodies within 5 half-life of investigational compound or those who have not recovered from adverse events due to agents administered more than 1 week earlier. Bisphosphonates, endocrine therapy, and trastuzumab are permitted without restriction.
- Patients who are receiving any other investigational agents.
- Previous treatment of the target lesions with radiation therapy.
- Patients who have previously been treated with whole brain radiation.
- History of allergic reactions attributed to compounds of similar chemical or biologic composition to TPI 287.
- Pregnant women are excluded from this study because TPI 287 is an agent with an unknown but potential risk for teratogenic or abortifacient effects. Because there is an unknown but potential risk for adverse events in nursing infants secondary to treatment of the mother with TPI 287, breastfeeding should be discontinued if the mother is treated with TPI 287.
- Known contraindication to enhanced MRI and CT scan.

 Uncontrolled intercurrent illness including, but not limited to, ongoing or active infection, symptomatic congestive heart failure, unstable angina pectoris, cardiac arrhythmia, uncontrolled seizure activity or psychiatric illness/social situations that would limit compliance with study requirements.

3.3 Inclusion of Women and Minorities

Both men and women of all races and ethnic groups are eligible for this trial.

4. INFORMED CONSENT PROCESS

Eligible patients will be evaluated by a multi-disciplinary team composed of radiation oncologists, neurosurgeons, and a medical oncologist. During their visit, either a physician or a research coordinator will explain the study to the patient. Informed consent form will be provided and if the patient agrees to participate, signed consent form will be obtained prior to participation.

Following registration, patients should begin protocol treatment within 7 days. If a patient does not receive protocol therapy following registration, the patient's registration on the study may be canceled.

5. TREATMENT PLAN

5.1 **Pre-Treatment Evaluation**

Patients will be evaluated by a multi-disciplinary team composed of medical/neuro oncologists, radiation oncologists, and neurosurgeons to assess for their eligibility. Patient's oncologic history, presenting symptoms, physical examination, pathology, extent of systemic disease, and imaging studies will be reviewed.

5.2 Fractionated stereotactic radiotherapy (FSRT)

Brain metastases will be delineated by gadolinium enhanced magnetic resonance imaging (MRI) (Siemens Sonata, Siemens Medical Systems, Erlangen, Germany) with 1 mm slices for treatment planning purposes performed within 2 weeks prior to the delivery of radiation (MRI Novalis protocol). If MRI Novalis is not possible, CT scan of the brain with contrast or other suitable MRI scan brain may be used for delineation of the brain metastases. Patient immobilization will be achieved by using a commercially available frameless head mask fixation system (BrainlabAG, Feldkirchen, Germany). The image planning data set will be co-registered and fused with 1-2mm slice thickness computed tomography (CT) imaging (General Electric Medical System, Milwaukee, WI) obtained at simulation. The gross tumor volume (GTV) will be designated by the edge of the tumor. The planning target volume (PTV) will include a 1 mm

expansion on the GTV. The prescription dose will be 25 Gy in 5 daily fractions delivered to the PTV. Planning will take place with the BrainLab treatment planning system and FSRT will be delivered via the Novalis linear accelerator with robotic table. Doses will be prescribed to ensure coverage of at least 95% of the PTV with the prescription dose. The maximum dose will not exceed 115% of the prescription dose. Treatments will be delivered using dynamic conformal arcs or intensity modulated radiotherapy (IMRT).

5.3 Drug therapy

TPI 287 will be administered on an outpatient basis. Reported adverse events and potential risks are described in Section 7. Appropriate dose modifications are described in Section 6.

TPI 287 Administrations

TPI 287 will be administered as an intravenous infusion over 60 minutes. A window of \pm 15 minutes will be permitted.

Patients will receive the TPI 287 once per week, for total of 3 doses. Treatment with TPI 287 will start the same day of starting FSRT treatment. On the day of FSRT, TPI 287 will be given 4 (+/-2) hours prior to FSRT.

In order to prevent any potential hypersensitivity reactions, all subjects must be premedicated prior to TPI 287 administration. The following drugs and dosing regimens are provided as guidelines for premedication, which must include a corticosteroid, an antihistamine, and an H2 blocker. The concomitant use of steroids in some subjects should be considered in determining the dose of an additional corticosteroid. Oral (PO) dosing as an alternative to IV dosing for premedication is acceptable where appropriate.

Premedication Regimen		
Dexamethasone*	20 mg PO at 12 hours prior and 20 mg PO at 6 hours prior	
Diphenhydramine	50 mg IV push prior	
H2 blocker	IV prior (e.g., Cimetidine 300 mg)	
*In the event that dexamethasone is not available, methylprednisolone may be		
substituted at an equivalent dose (4 mg methylprednisolone = 0.75 mg dexamethasone).		

Subjects will be closely monitored for signs and symptoms of a hypersensitivity reaction during the entire infusion of TPI 287, and 1 hour after completion of TPI 287 infusion. Vital signs will be measured every 30 minutes. If a mild-to-moderate (Grade 1 to 2) hypersensitivity reaction is observed, the TPI 287 infusion will be interrupted. Patient will receive intravenous diphenhydramine 50 mg, hydrocortisone IV 100 mg, and appropriate supportive care until the symptoms resolve. If the signs and symptoms resolve within 1 hour, the TPI 287 infusion will be restarted at a slower infusion rate (half that of the initial attempt), and this slower infusion rate will be used for the remainder of the trial. If the symptoms take longer to resolve, the infusion will not be restarted, and the next dose of TPI 287 will be administered 1 week after the

interrupted dose at a slower infusion rate (half of the rate at which hypersensitivity reaction occurred) pending all signs and symptoms of hypersensitivity have resolved. If a \geq Grade 3 hypersensitivity reaction is observed, the TPI 287 infusion will be stopped and appropriate supportive care administered until the symptoms resolve. The subject will be discontinued from the trial.

Dose Definition

Dose Escalation Phase:

The starting dose (i.e., dose level 1) will be 14 mg/m^2 /dose. Provided that MTD has not been reached, the TPI 287 dose will be increased as follows:

Dose Escalation Schedule		
Dose Level	Dose	
	TPI 287 IV	Radiotherapy
Level -2	5 mg/m ² /dose	5 Gy daily fraction
Level -1	7 mg/m ² /dose	5 Gy daily fraction
Level 1	14 mg/m ² /dose	5 Gy daily fraction
Level 2	28 mg/m ² /dose	5 Gy daily fraction
Level 3	56 mg/m ² /dose	5 Gy daily fraction
Level 4	85 mg/m ² /dose	5 Gy daily fraction
Level 5	113 mg/m ² /dose	5 Gy daily fraction
Level 6	$127.5 \text{ mg/m}^2/\text{dose}$	5 Gy daily fraction

Table 1. Dose Escalation Schedule

If dose level 1 is found to cause unacceptable toxicity, the dose will be de-escalated to levels -1 or -2.

Dose Expansion Phase:

The TPI 287 dose used in the dose expansion cohort will be MTD determined from the dose escalation phase. TPI 287 will be administered intravenously prior to treatment of brain metastasis with FSRT on day 1 and will be given for 2 more weekly doses. The prescription dose of FSRT will be 25 Gy in 5 daily fractions as described in section 5.2.

Definition of Maximum Tolerated Dose:

The maximum tolerated dose (MTD) is the highest dose of TPI 287 that does not cause unacceptable toxicity in more than one of six patients at that dose level. The MTD is defined as one dose level below the highest toxic dose (i.e., the DLT dose).

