5.4 Definition of Dose-Limiting Toxicity

Toxicities will be graded in severity according to the guidelines outlined in the NCI-CTCAE version 4.0. Dose limiting CNS and non-CNS (hematologic and non-hematologic) toxicities will be defined differently and will be based on events that occur during the study period. In order to be declared as dose-limiting toxicity, an adverse event must be related (definite, probable, or possible) to study treatment.

A dose-limiting toxicity (DLT) will be defined as any one of the following adverse events occurring within 8 weeks from last dose of radiation therapy:

CNS toxicities:

Acute CNS toxicities (occurring \leq 30 days after completing FSRT treatment):

• Any grade 3 or higher central nervous adverse events including but not limited to headache, dizziness, vertigo, new onset seizures, cerebral edema, cerebral hemorrhage, and new onset neurologic deficit.

Delayed onset CNS toxicities (occurring >30 days after completing FSRT treatment):

 Any grade 3 or 4 adverse event arising within the irradiated volume including but not limited to radiation necrosis or focal neurological deficits.

Non-CNS toxicities:

Non-hematologic toxicities:

- Any grade 3 or higher non-hematologic adverse event with the exception of alopecia, fatigue, and anorexia.
- Grade 3 or higher nausea and/or vomiting that persists ≥ 48 hours despite optimal medical management.

Hematologic toxicities:

- Grade 4 neutropenia lasting for \geq 7 days in duration
- Grade \geq 3 febrile neutropenia with/without infection

• Grade 4 thrombocytopenia

Dose escalation will be determined based on the occurrence of DLTs. For the purposes of determining whether to advance the dose levels, DLTs will be counted by patient. In the event of the development of any grade 3 or 4 toxicity felt to be at least possibly related to study drug, TPI 287 will be held until resolution to grade 1 or baseline assuming that occurs within 15 day window.

Dose escalation will follow the standard 3+3 design. The enrollment to next higher dose level will be delayed for 8 weeks after the completion of FSRT by the last patient enrolled at the dose level. This period of 8 weeks will allow monitoring potential delayed toxicities. Management and dose modifications associated with the above adverse events are outlined in Section 6. Dose escalation will proceed according to the following scheme. Dose-limiting toxicity (DLT) is defined above.

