Number of Patients with DLT at a Given Dose Level	Escalation Decision Rule
0 out of 3	Enter 3 patients at the next dose level.
≥2	Dose escalation will be stopped. This dose level will be declared the maximally administered dose (highest dose administered). Three (3) additional patients will be entered at the next lowest dose level if only 3 patients were treated previously at that dose.
1 out of 3 or ≥ 2 grade 2 CNS toxicities	 Enter at least 3 more patients at this dose level. If 0 of these 3 patients experience DLT, proceed to the next dose level. If 1 or more of this group suffer DLT, then dose escalation is stopped, and this dose is declared the maximally administered dose. Three (3) additional patients will be entered at the next lowest dose level if only 3 patients were treated previously at that dose.
≤1 out of 6 at highest dose level below the maximally administered dose	This is the dose to be used in the expanded cohort and will be considered recommended phase 2 dose. At least 6 patients must be entered at this dose.

Table 2. Dose Escalation Rules

If dose level 1 is found to cause unacceptable toxicity, the dose will be de-escalated to level -1 (7 mg/m^2). Three patients will be enrolled at dose level -1. If no DLT is observed, three additional patients will be enrolled at dose level -1 such that safety is established in at least 6 patients prior to entering dose expansion phase.

Any delayed CNS-toxicity arising within the radiation field but seen beyond the window for DLT registration (> 8weeks following completion of FSRT) will be recorded. Furthermore, occurrence of any delayed-onset treatment related grade 3 or higher central nervous toxicity at any time (during and after DLT period of 8 weeks) will lead to holding dose-escalation and adding 3 patients to the dose level at which toxicity has occurred. Occurrence of additional delayed-onset treatment related grade 3 or higher CNS- toxicity will be reviewed with Protocol Monitoring Committee and IRB to determine whether discontinuation or modification of trial is subsequently warranted.

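### The MTD definition in 5.3 contradicts itself when a backfilled level shows two or more DLTs in six, and Table 2 has no end-of-ladder rule for 0/3 at level 6

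*Combined protocol and SAP*

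**What the plan says.** All references are to the combined protocol and SAP.

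- **5.3, MTD definition, first sentence:** the MTD is "the highest dose of TPI 287 that does not cause unacceptable toxicity in more than one of six patients at that dose level".
- **5.3, MTD definition, second sentence:** "The MTD is defined as one dose level below the highest toxic dose (i.e., the DLT dose").
- **5.3, Dose Expansion Phase:** "The TPI 287 dose used in the dose expansion cohort will be MTD determined from the dose escalation phase".
- **5.4, Table 2, 0/3 row:** "Enter 3 patients at the next dose level".
- **Table 2, row for two or more DLTs:** escalation stops. "This dose level will be declared the maximally administered dose (highest dose administered"). The level below receives three more patients if it had only three.
- **Table 2, row for 1/3 or two or more grade 2 CNS toxicities (row 3):** at least three more patients enter. "If 0 of these 3 patients experience DLT, proceed to the next dose level". One or more DLTs among them stops escalation.
- **Table 2, last row:** the expansion dose and recommended phase 2 dose (RP2D) needs at most 1 "out of 6 at highest dose level below the maximally administered dose", with at least six patients entered there.
- **5.4, observation period:** "The enrollment to next higher dose level will be delayed for 8 weeks after the completion of FSRT" by the last patient at the current level.
- **5.4, text below Table 2:** for level -1 only, three patients without DLT are followed by three more, so that six support safety before expansion.
- **14.1 and 14.2:** the MTD is a primary endpoint. Escalation has a maximum of 36 patients. Expansion brings the MTD level to 10, counting those already treated there.

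Level 6, the last level, is 127.5 mg/m², which section 2.2 reports as the single-agent weekly MTD.

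**The concern.** A 3+3 rule should give one answer for every outcome it can reach. Two reachable outcomes fail that test.

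**(a) Rejected backfill.** Level k is toxic, and level k-1, filled to six, also shows at least 2/6 DLTs. The highest toxic dose is still k, so the second sentence makes k-1 the MTD. The first sentence and the last row of Table 2 both exclude k-1. Since 5.3 makes the MTD the expansion dose, one sentence of the plan would send further patients to a dose that its own threshold rejects.

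**(b) Tolerated level 6.** Both escalation rows send the trial on to a level that does not exist. The last row of Table 2 and the second sentence each need a toxic level above the selected one, so neither can choose level 6. The first sentence can. After 1/3, row 3 already brings level 6 to six patients. The open case is 0/3. No text says to enter three more and observe them before expansion, and the 8-week hold is tied to opening a higher level. An improvised decision would then settle a primary endpoint and the expansion dose.

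**Working it through.** **The plan's own figure.** Levels 1 to 6 with at most six patients each give 6 × 6 = 36, the stated maximum. Enumerating every Table 2 path also gives 36.

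**Inputs.** The decision rules come from Table 2, with the row for two or more DLTs re-applied at backfilled levels. The documents give no DLT or grade 2 CNS rates, so these DLT rates for levels 1 to 6 are assumptions:

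- A: 2, 4, 7, 10, 14, 17%
- B: 3, 6, 10, 17, 25, 33%
- C: 5, 10, 15, 22, 30, 40%
- D: 5, 10, 18, 28, 39, 50%

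**Formulas.** At a level with DLT rate p:

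- q0 = (1-p)³ and q1 = 3p(1-p)².
- t = probability that at least two of three patients have grade 2 CNS toxicity. It is 0, 0.104 and 0.352 at grade 2 rates of 0, 20 and 40%.
- Escalate on three patients: q0(1-t).
- Escalate on six patients: q1·q0 + q0·t·q0.
- Outcome (a): level k-1 cleared on three, level k stops, and at least two of the three backfilled patients have a DLT. This is summed over k = 2 to 6.

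**Results without grade 2 triggers.**

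| | A | B | C | D |
|---|---|---|---|---|
| Outcome (a) | 1.1% | 4.5% | 6.1% | 7.9% |
| Level 6 cleared | 54% | 17% | 7% | 2% |
| Cleared on three patients only | 40% | 12% | 5% | 1% |
| P(at least 2 DLTs in patients 4-6) | 0.077 | 0.255 | 0.352 | 0.500 |
| Fill to six changes the selected dose | 3.1% | 3.1% | 1.8% | 0.7% |
| Level 6 accepted if reached: 0/3 enough | 77% | 43% | 31% | 17% |
| Level 6 accepted if reached: filled to six | 73% | 36% | 23% | 11% |

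The fifth row is the third times the fourth. For curve A, 0.4015 × 0.0769 = 0.031.

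**With grade 2 triggers (range over the curves).** At a 20% grade 2 rate, level 6 clears in 2-48% of trials, on three patients in 1-33%, and (a) occurs in 1-7%. At 40% the ranges are 1-36%, 0.5-19% and 1-5%.

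**DLTs avoided at level 6.** Filling to six still treats patients 4-6. It spares patients 7-10, and only when at least two of patients 4-6 have a DLT. The expected number avoided per trial that clears on 0/3 is 4p × P(at least 2 of 3):

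- A: 4 × 0.17 × 0.077 = 0.05
- B: 4 × 0.33 × 0.255 = 0.34
- C: 4 × 0.40 × 0.352 = 0.56
- D: 4 × 0.50 × 0.500 = 1.0

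Multiplied by the chance of clearing on three patients, this is about 0.01-0.04 DLT per trial.

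**Precision.** The one-sided 95% upper limit for the DLT rate is 1 - 0.05^(1/3) = 63% after 0/3 and 1 - 0.05^(1/6) = 39% after 0/6. It is 58% after 1/6 (Clopper-Pearson).

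**The case against.** The strongest reply is that the plan already contains the right principle. The first sentence tests the MTD on six patients, 5.4 calls the design a standard 3+3, the last row of Table 2 asks for at least six, and a maximum of 36 leaves room for six at level 6. On (a), three rules agree and only the second sentence dissents, so a team following Table 2 would not expand at a rejected level. This largely stands. It makes (a) a conflict of wording, and it makes (b) a missing instruction rather than a missing principle. It does not close 0/3 at level 6: the six-patient requirement sits in a row that a tolerated level 6 cannot trigger, 36 is a ceiling, and the fill step is written out only for level -1.

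Four stronger inferences are tempting, and the documents do not support them.

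- **That no rule can select or fill level 6.** The first sentence can select it, and row 3 fills it after 1/3.
- **That DLTs in patients 4-6 would go uncounted.** The row for two or more DLTs states no denominator, so it can be read as covering six patients at level 6, as it is read for a backfilled level. Monthly committee review (12.2) and the late CNS rules (5.4, 5.9) also remain.
- **That the plan directs expansion to level 5.** This takes the gloss in Table 2 about the highest dose administered out of a row describing a level that has just been stopped.
- **That the harm is all the DLTs expected in patients 4-10, or 7p.** Most of those patients are treated under either rule.

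**Conclusion.** The point holds in limited form. The second MTD sentence in 5.3 contradicts the first sentence and the last row of Table 2 when a backfilled level shows at least 2/6. Table 2 also lacks an end-of-ladder rule, which leaves 0/3 at level 6 unresolved.

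Both outcomes are reachable, and they trade off: mild toxicity makes a tolerated level 6 likely, while steeper toxicity raises the chance of a rejected backfill. The sizes rest entirely on the assumed curves and should be read as ranges. The practical effect on dose selection is small, and a reader might infer from the 63% upper limit that it is larger. That limit applies to any three-patient cohort with no DLT. The case for acting is that rules for a primary endpoint should not conflict or run out, and that the repair is cheap. This is a should-fix; the documents do not support a higher grade.

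**What to change.** 1. **5.3:** delete the second MTD sentence. State that the MTD/RP2D is the highest level, below any level declared the maximally administered dose, with at least six evaluable patients and no more than one DLT in the first six, and that level 6 is the dose if it meets this. DLTs in patients added under the late CNS rule are handled by that rule.
2. **Table 2, new row for level 6:** after 0/3 without the row 3 trigger, enter three more and observe them for 8 weeks after FSRT. At most 1/6 selects level 6. At least 2/6 makes it the maximally administered dose, and level 5 is filled to six. If row 3 applies, no DLT in the added three selects level 6; otherwise row 3 stops escalation as now.
3. **Table 2, backfill:** a backfilled level with at least 2/6 is rejected and the next lower level is filled to six. If level 1 is rejected, follow the existing level -1 rule, three patients and then three more.

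**Cost.** Part (a) is wording only and adds no patients beyond Table 2 re-applied. Part (b) adds three patients and one 8-week observation period after 0/3 at level 6; those patients count toward the 10 if level 6 is selected. If level 6 is then rejected, level 5 takes three more where only three were treated, and expansion starts later. Without grade 2 triggers, mean escalation size rises by 1.3, 0.4, 0.2 and 0.1 patients on curves A to D. A level 6 with a true 17% DLT rate is accepted slightly less often once reached (73% against 77%). The maximum of 36 is unchanged.

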5.4 Definition of Dose-Limiting Toxicity

Toxicities will be graded in severity according to the guidelines outlined in the NCI-CTCAE version 4.0. Dose limiting CNS and non-CNS (hematologic and non-hematologic) toxicities will be defined differently and will be based on events that occur during the study period. In order to be declared as dose-limiting toxicity, an adverse event must be related (definite, probable, or possible) to study treatment.

A dose-limiting toxicity (DLT) will be defined as any one of the following adverse events occurring within 8 weeks from last dose of radiation therapy:

CNS toxicities:

Acute CNS toxicities (occurring \leq 30 days after completing FSRT treatment):

• Any grade 3 or higher central nervous adverse events including but not limited to headache, dizziness, vertigo, new onset seizures, cerebral edema, cerebral hemorrhage, and new onset neurologic deficit.

Delayed onset CNS toxicities (occurring >30 days after completing FSRT treatment):

 Any grade 3 or 4 adverse event arising within the irradiated volume including but not limited to radiation necrosis or focal neurological deficits.

Non-CNS toxicities:

Non-hematologic toxicities:

- Any grade 3 or higher non-hematologic adverse event with the exception of alopecia, fatigue, and anorexia.
- Grade 3 or higher nausea and/or vomiting that persists ≥ 48 hours despite optimal medical management.

Hematologic toxicities:

- Grade 4 neutropenia lasting for \geq 7 days in duration
- Grade \geq 3 febrile neutropenia with/without infection

• Grade 4 thrombocytopenia

Dose escalation will be determined based on the occurrence of DLTs. For the purposes of determining whether to advance the dose levels, DLTs will be counted by patient. In the event of the development of any grade 3 or 4 toxicity felt to be at least possibly related to study drug, TPI 287 will be held until resolution to grade 1 or baseline assuming that occurs within 15 day window.

Dose escalation will follow the standard 3+3 design. The enrollment to next higher dose level will be delayed for 8 weeks after the completion of FSRT by the last patient enrolled at the dose level. This period of 8 weeks will allow monitoring potential delayed toxicities. Management and dose modifications associated with the above adverse events are outlined in Section 6. Dose escalation will proceed according to the following scheme. Dose-limiting toxicity (DLT) is defined above.

Number of Patients with DLT at a Given Dose Level	Escalation Decision Rule
0 out of 3	Enter 3 patients at the next dose level.
≥2	Dose escalation will be stopped. This dose level will be declared the maximally administered dose (highest dose administered). Three (3) additional patients will be entered at the next lowest dose level if only 3 patients were treated previously at that dose.
1 out of 3 or ≥ 2 grade 2 CNS toxicities	 Enter at least 3 more patients at this dose level. If 0 of these 3 patients experience DLT, proceed to the next dose level. If 1 or more of this group suffer DLT, then dose escalation is stopped, and this dose is declared the maximally administered dose. Three (3) additional patients will be entered at the next lowest dose level if only 3 patients were treated previously at that dose.
≤1 out of 6 at highest dose level below the maximally administered dose	This is the dose to be used in the expanded cohort and will be considered recommended phase 2 dose. At least 6 patients must be entered at this dose.

Table 2. Dose Escalation Rules

If dose level 1 is found to cause unacceptable toxicity, the dose will be de-escalated to level -1 (7 mg/m^2). Three patients will be enrolled at dose level -1. If no DLT is observed, three additional patients will be enrolled at dose level -1 such that safety is established in at least 6 patients prior to entering dose expansion phase.

Any delayed CNS-toxicity arising within the radiation field but seen beyond the window for DLT registration (> 8weeks following completion of FSRT) will be recorded. Furthermore, occurrence of any delayed-onset treatment related grade 3 or higher central nervous toxicity at any time (during and after DLT period of 8 weeks) will lead to holding dose-escalation and adding 3 patients to the dose level at which toxicity has occurred. Occurrence of additional delayed-onset treatment related grade 3 or higher CNS- toxicity will be reviewed with Protocol Monitoring Committee and IRB to determine whether discontinuation or modification of trial is subsequently warranted.

